13.3 SAFETY ENDPOINTS

• The proportion of patients developing treatment-emergent hematological and nonhematological adverse events for the combination of ruxolitinib and enasidenib.

13.4 EXPLORATORY ENDPOINTS

- The proportion of patients who achieve improvement quality of life as assessed by the by the Myelofibrosis Symptom Assessment Form (MF-SAFv4.0) with the combination of ruxolitinib and enasidenib
- Assess the pharmacodynamics of ruxolitinib and enasidenib when combined in this population.
- Assess the effects of combined therapy on gene expression and global methylation status.
- Assess changes in mutant allele burden and clonal architecture of disease.

14.0 STUDY PROCEDURES

Study Design

MPN-RC

This is a multicenter, Phase II trial designed to assess the effect of ruxolitinib and enasidenib combination in subjects with accelerated or blast-phase MPN and subjects with chronic phase Primary Myelofibrosis, Post Polycythemia Vera, or Post Essential Thrombocythemia Myelofibrosis (PMF, post-PV MF, or post-ET MF) with 4-9% blasts. Patients will receive ruxolitinib and enasidenib orally on days 1-28 of a 28-day cycle.

Specifically, a Phase II Simon min-max design will be conducted in accelerated or blast-phase MPN patients (20 patients) and a descriptive cohort of up to 9 chronic phase patients.

Intervention

Patients who meet eligibility criteria will be treated with ruxolitinib and enasidenib orally on days 1-28 of a 28-day cycle. Cycles will be continued until the patient wishes to be removed from the study, unacceptable toxicity develops, disease progression, treating physician recommends removal, or termination of study occurs.

14.1 SCREENING/BASELINE PROCEDURES

Assessments performed exclusively to determine eligibility for this study will be done only after obtaining informed consent. Assessments performed for clinical indications (not exclusively to determine study eligibility) may be used for baseline values even if the studies were done before informed consent was obtained.

All screening procedures must be performed within 30 days prior to registration unless otherwise stated. The screening procedures include:

• Patient Informed Consent

Before a patient undergoes screening, a medically qualified member of the Study Team who has been specifically trained in the implementation of this Protocol during the Site Initiation Visit or thereafter, such as the Site Principal Investigator, any of the co-Investigators, or a Clinical

in Patients with Accelerated/Blast-phase Myeloproliferative Neoplasm or Chronicphase Myelofibrosis with an IDH2 Mutation

(Myeloproliferative Neoplasms Research Consortium [MPN-RC] 119)

Research Nurse must obtain documented consent from each potential patient prior to participating in a clinical trial.

Consent must be documented by the patient's dated signature or by the patient's legally acceptable representative's dated signature on a consent form along with the dated signature of the person conducting the consent discussion. A copy of the signed and dated consent form should be given to the patient before participation in the trial.

The initial informed consent form, any subsequent revised written informed consent form and any written information provided to the patient must receive the IRB/EC's approval/favorable opinion in advance of use. The patient or his/her legal representative should be informed in a timely manner if new information becomes available that may be relevant to the patient's willingness to continue participation in the trial. The communication of this information will be provided and documented via a revised consent form that captures the patient's or legal representative's dated signature. The informed consent will adhere to IRB/EC requirements, applicable laws and regulations and Sponsor requirements.

- Demographics (age, gender, race, ethnicity)
- Medical History (A medical history will be obtained by the Investigator or qualified designee. Medical history will include all active conditions, and any condition diagnosed within the prior 10 years that are considered to be clinically significant by the Investigator. Details regarding the disease for which the patient has enrolled in this study will be recorded separately and not listed as medical history).
- Prior Treatment Details (The Investigator, or qualified designee, will review all prior cancer treatments including systemic treatments, RT and surgeries)
- Bone marrow biopsy and aspirate with cytogenetics and molecular genetic profiling for presence of JAK2 (or MPL or CALR mutation status in the case that no JAK2 mutation is detected) as well as IDH2 mutation status. Bone marrow biopsy obtained within 84 days prior to screening in the absence of disease modifying therapy may be used for determining eligibility. Mutational profiling may be carried out at local laboratories and does not require central laboratory confirmation.
- Physical exam including vital signs, body weight and height, and spleen and liver measurements
- Transfusion history for 3 months prior to Day 1
- Review previous concomitant medications within 90 days of screening and all myeloproliferative neoplasms directed therapies since time of diagnosis
- Complete Blood Count (CBC) with differentials (includes platelet count)
- Chemistries (LDH, total and direct bilirubin, phosphorus, albumin, uric acid, Na, K, Cl, Mg, CO2, BUN, Cr, glucose (random), Ca, AST, ALT, Alk Phos, total protein)
- Lipid Panel
- Urinalysis
- Pregnancy test, urine or blood, with a sensitivity of at least 50 mIU/mL (for FCBP only)
- Eastern Cooperative Oncology Group (ECOG) performance status
- ECG

MPN-RC

- Spleen volume assessment by CT scan or MRI
- Cardiac function assessment (LVEF) by ECHO or MUGA
- Review patient eligibility criteria

14.2 REGISTRATION PROCEDURES

Only MPN-RC approved centers may participate and register patients to this study.

in Patients with Accelerated/Blast-phase Myeloproliferative Neoplasm or Chronicphase Myelofibrosis with an IDH2 Mutation

(Myeloproliferative Neoplasms Research Consortium [MPN-RC] 119)

To register a potential participant, complete the Registration Form for the trial located at the study REDCap link provided by the Mayo Statistical Data Center. This form confirms eligibility criteria and informed consent and contains basic demographic and clinical information. Once eligibility is confirmed and informed consent has been obtained, registration of a patient in the trial can occur. After completion of this form, a unique patient ID will be assigned by the system. An email notification will be sent to the MPN-RC Administrative and Statistical and Data Center core for each registered patient.

14.2.1 SITE REGISTRATION WITH MPN-RC

MPN-

Before an MPN-RC institution can enroll patients, protocol specific regulatory documents must be submitted to the MPN-RC Central Coordinating Office via E-mail (PDF file preferred) or fax:

> MPN-RC Central Coordinating Office [contact] [contact] [contact]

Required Protocol Specific Regulatory Documents (E-mailed by PDF format preferred):

- 1. Submit a copy of IRB approval for MPN-RC 119
- 2. Submit a copy of the IRB approved consent form for MPN-RC 119
- 3. Submit a copy of the CV of the investigational pharmacist and Pharmacy license
- 4. Submit a copy of the site's drug destruction policy
- 5. Submit a copy of a signed and dated CV and medical license of the Principal Investigator
- 6. Submit a copy of Form FDA 1572 as completed by the Principal Investigator

Before an MPN-RC institution can enroll patients, please contact the Clinical Central Office (e-mail: [contact]), to ensure that a slot is available for enrollment prior to approaching a patient about possible participation in this trial.

This study uses the MPN-RC on-line Patient Registration system (https://redcap2.mayo.edu/redcap/). Registration will be accepted only through use of the MPN-RC database. Registration must occur prior to the initiation of therapy.

Confirm eligibility criteria and complete the on-line Registration Worksheet.

If the registering clinical research coordinator (CRC) requires assistance, he/she may consult the on-line help file located under the Help menu of the MPN-RC application or call the central office.

When the patient is registered to MPN-RC 119, a patient identification number will be generated. Registration will not be completed if eligibility requirements are not met for the selected trial.

The registering institution will receive a Confirmation of Registration email from the database that should be printed and included in the patient chart. If a registering institution needs to correct the registration form, contact the MPN-RC Statistics and Data Center at Mayo ([contact]) and the Clinical Central Office: E-mail: [contact].

Before Study Drug Shipment

in Patients with Accelerated/Blast-phase Myeloproliferative Neoplasm or Chronicphase Myelofibrosis with an IDH2 Mutation

(Myeloproliferative Neoplasms Research Consortium [MPN-RC] 119)

Before Study Drug can be shipped to the MPN-RC center to begin accruing patients, the above regulatory documents are required to be emailed to the MPN-RC Central Office to the attention of the Clinical Trials Manager, as noted above.

14.3 INFORMED CONSENT

The patient must be aware of the neoplastic nature of his/her disease, as well as of the expected life expectancy at his/her stage of disease. The patient must willingly consent after being informed of the procedures to be followed, the experimental nature of the therapy, alternatives, potential benefits, side effects, risks, and discomforts. BRANY Institutional Review Board (or other local ethics committees for non-US sites) approval of this protocol and of its consent form is required.

14.4 DATA MANAGEMENT

After registration of a patient, additional case report forms in the study database will be available for completion according to the Schedule of Events (Table 4). All clinical data and obtained specimens will be labeled with the patient ID assigned at registration for the entire duration of the subject's participation.

Data for all clinical variables will be stored in the REDCap database. Access to the REDCap database will be limited to MPN-RC investigators and designees; users at each site will only be able to view the records pertaining to subjects enrolled at their particular site.

15. TREATMENT PERIOD

The subject must be enrolled into the study, at the latest 30 days from signing the ICF, following Sponsor review of eligibility. The Treatment Period begins at Cycle 1 Day 1 and ends at the End-of-Treatment Visit. During the Treatment Period, all subjects will be closely monitored for safety. Toxicities (AEs and laboratory abnormalities) will be evaluated and graded according to the CTCAE. During this period the following assessments should occur:

- Bone marrow biopsy and aspirate with cytogenetics and molecular genetic profiling for presence of JAK2 (or MPL or CALR mutation status in the case that no JAK2 mutation is detected) as well as IDH2 mutation status. This is done at C4 D1 (for all accelerated patients, may be done at the discretion of the Investigator for chronic phase patients), C7 D1 (for all patients), C10 D1(for accelerated phase patients, may be done at the discretion of the Investigator for chronic phase patients), and every 6 cycles, thereafter (for all patients).
- Transfusion history will be collected on Day of each cycle
- Pregnancy Test
- A physical exam including a review of current medical conditions and medications
- Vital signs (heart rate, breathing rate, blood pressure, temperature, weight, and height)
- ECOG performance status
- Adverse events and concomitant medications
- Complete blood counts and serum chemistry
- Spleen volume assessment by CT/MRI at C7 D1, and C10 D1
- ECG, day 1 of each cycle until Cycle 7
- Research blood sample collection
- MF-SAFv4.0 questionnaire (paper or electronic)
- Enasidenib administration
- Medication diary collected and new one dispensed

in Patients with Accelerated/Blast-phase Myeloproliferative Neoplasm or Chronicphase Myelofibrosis with an IDH2 Mutation

(Myeloproliferative Neoplasms Research Consortium [MPN-RC] 119)

15.1 END OF TREATMENT VISIT

The post-treatment period includes the time after the End of Treatment Visit until the End of Study Visit. This period is 30 days. The following assessments should occur:

- Bone marrow biopsy and aspirate with cytogenetics and molecular genetic profiling for presence of JAK2 (or MPL or CALR mutation status in the case that no JAK2 mutation is detected) as well as IDH2 mutation status. Mutational profiling may be carried out at local laboratories and does not require central laboratory confirmation.
- Physical exam
- Vital signs, body weight and height, and spleen and liver measurements
- Concomitant medications and adverse events
- CBC and differentials
- Serum chemistry
- ECG

MPN-RC

- Spleen volume assessment by CT scan or MRI
- Research blood sample collection
- MF-SAFv4.0 questionnaire (paper or electronic)

15.2 END OF STUDY VISIT

The visit is the mandatory safety follow-up visit and should be conducted approximately 30 days after the end of trial treatment or before the initiation of a new anti-cancer treatment, whichever comes first. All AEs that occur prior to the End of Study Visit should be recorded.

MPN-RC

A Phase II Open-label Study of Combined Ruxolitinib and Enasidenib

in Patients with Accelerated/Blast-phase Myeloproliferative Neoplasm or Chronicphase Myelofibrosis with an IDH2 Mutation

(Myeloproliferative Neoplasms Research Consortium [MPN-RC] 119) Table 4. Schedule of Events

	Screening	Cycle1-2				Cycle 3-6	Cycle 7 and beyond	End of treatment	End of	Survival
Procedure	Period	Day 1 ⁵	Day 8	Day 15	Day 22	Day 1	Day 1		Study ¹¹	Follow Up
Informed Consent	Х									
Medical History (including prior MF-directed therapies)	Х									
Physical examination ¹	Х	X		X		Х	Х	Х	Х	
Transfusion History	X ²	X ²				Х	X	Х	Х	
Pregnancy test (for FCBP only) ³	Х	X	x	X	X	Х	Х	Х	Х	
CBC and differentials	Х	X	X	X	X	Х	X	Х	Х	
Serum Chemistry ⁴	X	X	X	X	X	Х	X	Х	Х	
Urinalysis	X									
12-LeadECG ¹⁴	Х	X	x	X	x	Х	X	Х	Х	
Echo/MUGA	X									
Bone Marrow Aspirate and Biopsy ^{6,7}	X ⁶					X ^{6,7}	X ^{6,7}		X^6	
Biospecimen Collection– Peripheral blood	X ¹²	X ¹²				X ¹²	X ¹²		X ¹²	
Adverse event evaluation		X		X		Х	X	Х	Х	
Concomitant medications, therapies, and procedures evaluation	Х	X		X		X	X	Х	Х	
Spleen Volume Assessment ⁸	Х						X ⁸		Х	
Response Assessment							X ^{9, 13}		X	

ount The Tisch Cancer Institute

A Phase II Open-label Study of Combined Ruxolitinib and Enasidenib Sinai

in Patients with Accelerated/Blast-phase Myeloproliferative Neoplasm or Chronicphase Myelofibrosis with an IDH2 Mutation

(Myeloproliferative Neoplasms Research Consortium [MPN-RC] 119)

Nail Clippings	Х									
Study drug dispensing ¹⁰		X				Х	Х			
MF-SAFv4.0 Survey		X	X	X	X	Х	Х	Х	Х	
Survival Data ¹⁵										Х

- 1. Includes vital signs, weight, height and measurements of the spleen and liver. Height is only required at screening.
- 2. Subjects must have 3 months documented transfusion history prior to Day 1.
- 3. Pregnancy test, urine or blood, with a sensitivity of at least 50 mIU/mL, within 10 14 days prior to and again within 24 hours of starting enasidenib; then every week x 4, then monthly for all FCBP with regular menstrual cycles, or every 2 weeks if irregular cycles.
- 4. Includes sodium, potassium, chloride, carbon dioxide, blood urea nitrogen, creatinine, total bilirubin, alanine aminotransferase, , and glucose. Magnesium, , PT/PTT and INR need to only be done at screening. Lactate dehydrogenase uric Acid, phosphorus need to be checked day 1 of every cycle and in the EOS
- 5. If not done within 3 days of Day 1.
- 6. Bone Marrow Aspirate and Biopsy to be collected at baseline (within 84 days from screening is also permissible with permission from the Study Chair), Cycle 4 day 1 (at the discretion of the Investigator for chronic phase patients), Cycle 7 day 1, Cycle 10 day1(at the discretion of the Investigator for chronic phase patients), every 6 cycles, thereafter, and at the end of study visit. Peripheral blood draws may be used to perform JAK2 mutation testing if the bone marrow is not aspirable.
- 7. May be omitted if so decided by the treating physician. Should be done to confirm complete response and when clinically indicated.
- 8. CT scan or MRI to be performed at baseline, Cycle 7, Cycle 10, and at the end of study.
- 9. Response assessments (IWG-MRT criteria 2013 and ELN revised response criteria) should be after 6 cycles and every 3 6 cycles thereafter for the remainder of the study.
- 10. Collect pill diaries and any unused study drug to review for compliance prior to each cycle through cycle 24. After cycle 24, review patient drug diaries for ruxolitinib and enasidenib at each protocol visit.
- 11. The discontinuation visit will be considered as such on the date the patient is taken off treatment. The patient will have an end of study visit approximately 30 days after the end of trial treatment to assess for AEs.
- 12. Peripheral blood biomarker samples will be collected at screening, and day 1 of Cycle 1 -Cycle 7, every 3 cycles thereafter, and at the end of study, in conjunction with standard-of-care blood draws. Bone marrow aspirate samples will be collected whenever a bone marrow examination is scheduled to take place as designated in item 6 above.
- 13. Interval Milestone Response assessment can be performed at the beginning of any cycle after Cycle 1 if specific milestones are achieved as specified in study timeline.
- 14. ECGs done day 1 of each cycle until Cycle 7, ECGs should be done at EOS.\
- 15. Patients will continue to be followed for long term survival every 3 months by telephone encounter or medical record review to determine the following variables: alive versus deceased and type of current therapy. Patients will be followed for this long term survival data until death, confirmed lost to follow up, or a maximum of 1 year after end of treatment.

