10.7 DISCONTINUATION OF RUXOLITINIB AND ENASIDENIB

Upon planned discontinuation of ruxolitinib it is recommended to taper off the drug over the course of 4-7 days and permissible to use prednisone daily during this period to blunt rebound of symptoms. Since patients will be on varying dosing regimens of ruxolitinib, investigators are urged to discuss the ruxolitinib taper plan with Study Chairs.

If a patient has to have ruxolitinib held abruptly for the occurrence of adverse events (e.g. major bleeding, significant thrombocytopenia, etc.), then the ruxolitinib may be stopped WITHOUT a taper and a pulse of prednisone may be utilized if deemed necessary by the Investigator.

Enasidenib may be interrupted or stopped without tapering.

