	Aspirate Biomarkers ³	2 to 5 mL of bone marrow aspirate in a green top, heparinized tube (BD catalog #366480)	Х		Х	Х
one Ma	Biopsy Histopathology	One (1) H&E stain	Х		Х	Х
ă		One (1) Iron stain	Х		Х	Х
		One (1) Silver impregnated reticulin stain	Х		Х	Х
		Three (3) Unstained paraffin- fixed slides each with at least 2 sections	Х		Х	Х

The Tisch Cancer Institute

A Phase II Open-label Study of Combined Ruxolitinib and Enasidenib Sinai

in Patients with Accelerated/Blast-phase Myeloproliferative Neoplasm or Chronicphase Myelofibrosis with an IDH2 Mutation

	(Myclopio	miciative recipiasins research)
	Sample		Baseline	Cycle 1-6 Day 1	Cycle 4, 7, 10, day 1 and every 3 cycles ⁴	End of study ⁵
		If no aspirate, two (2)air dried unstained touch preps, 8 touches/slide, 2 horizontal	х		Х	Х
	Histopathology	Four (4) Unstained peripheral blood films, thin smears	Х		Х	Х
l Blood	Cytogenetics ²	If no BM aspirate karyotypic analysis ¹	Х		Х	Х
Periphera	Biomarkers ³	Three (3) ACD: yellow (BD# 364606; 8.5 mL)	Х	Х	Х	X
Other	Nails	2 to 10 clippings (pre-treatment, at enrollment only)	X			

(Myeloproliferative Neoplasms Research Consortium [MPN-RC] 119)

- All slides MUST BE LABELED properly. Labels are to include the patient's ID number, protocol number, time of study (e.g., baseline), type of specimen (e.g., BM biopsy, BM aspirate, blood), type of stain (e.g., Iron, H& E). For unstained slides, use a pencil to label the slides. All slides are to be sent to [name] at the NYBC in a labeled slide box. The label on the box is to include the patient's ID, protocol number, and time of study.
- 2. Cytogenetic analyses are performed as a standard of care. Karyotypic analysis of unstimulated bone marrow after direct 24 and 48 hours, if available, or peripheral blood shall be performed. Karyotypic analysis using G-banding technology is required.
- 3. All tissue samples must be registered via the MPN-RC on-line Patient Registration system (https://redcap2.mayo.edu/redcap/ the day they are collected and prior to shipment. All tubes, and envelopes (nails) must be labeled with patient's ID number, protocol number, time of study (e.g. baseline), type of specimen (e.g. BM biopsy, BM aspirate, blood) and date of collection.
- 4. BMB is optional for cycles 4 and 10 at the discretion of the Investigator for chronic phase patients
- 5. At relapse/progression or termination of study drug (that is off study drug for any reason).

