20.1 ACCELERATED / BLAST-PHASE COHORT

Primary endpoint: The primary endpoint of this study is best overall response, defined as partial response or better (CR+PR+Cri), and will be defined as the best response within 6 cyclesof combination therapy. All patients meeting the eligibility criteria who have signed a consent form and have begun treatment will be evaluable for response. Any evaluable patient not meeting the definition for response will be deemed as having a non-response.

Design: The largest overall response rate where the proposed combination treatment regimen would be considered ineffective in this patient population is 5%, and the smallest response rate that would warrant subsequent studies with the proposed regimen is 25%. This is based on retrospective analysis applying the 2013 IWG Response Criteria to patients treated with ruxolitinib¹. A Simon's two-stage minimax design will be employed to test the null hypothesis that the true overall response rate in this patient population is at most 5%.

Decision Rule: Enter 13 patients into the study. If 0 responses are observed in the first 13 patients (Stage 1), we may consider this regimen ineffective in the patient population and the trial will close due to a lack of efficacy. If 1 or more responses are observed in the first 13 evaluable patients, we will proceed to Stage 2 and enroll an additional 7 patients onto the study for a total of 20 patients. After completion of both stages, if 3 or more responses out of the 20 patients are observed, the combination therapy will be considered promising for further investigation.

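### Table 4 places the exit marrow and only exit response assessment about 30 days off drug, in conflict with 15.1 and Table 5, so some accelerated/blast-phase responses may go undocumented

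*Combined protocol and SAP*

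**What the plan says.** Three places in the protocol describe what is collected when a patient leaves treatment.

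- **Table 4 (Schedule of Events).** The End of Treatment column is empty for bone marrow, spleen volume and response assessment; the End of Study column is marked for all three. Footnote 6 repeats this for marrow ("every 6 cycles, thereafter, and at the end of study visit") and footnote 8 for imaging. Footnote 9 says formal response assessments "should be after 6 cycles", and the Cycle 3-6 column has none. Footnote 11 and 15.2 put End of Study at about 30 days after treatment ends; 15.2 brings it forward if a new anti-cancer treatment is about to start. Section 11.1 also uses 30 days, with a 7-day window.
- **Section 15.1 (End of Treatment Visit).** The list includes marrow and "Spleen volume assessment by CT scan or MRI". It does not include a response assessment. Its opening sentence describes the 30-day period up to End of Study, so the timing of the list is unclear.
- **Table 5, footnote 5.** The last column is titled as end of study, but the footnote defines it as "At relapse/progression or termination of study drug (that is off study drug for any reason". Under Table 7 (26.9), the marrow and cytogenetic forms follow Table 5.

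The primary endpoint (13.1, 20.1) is best response of CR, PR or CRi within six cycles. An evaluable patient who does not meet the definition counts as a non-responder.

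**The concern.** A site following Table 4 and a site following Table 5 would take the exit marrow about 30 days apart. Under Table 4, a patient who stops before C7D1 has no scheduled formal response assessment until the End of Study visit, which footnote 11 describes as a check for adverse events.

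This could reach the primary endpoint. CR and PR in Appendix B require resolved symptoms and a spleen that cannot be felt. Section 10.7 expects symptoms to return when ruxolitinib is withdrawn: during the taper it is "permissible to use prednisone daily during this period to blunt rebound of symptoms". A response present on the last day of treatment may therefore not be visible a month later, and would then be scored as a non-response.

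The decision rule turns on single responses: 0 versus 1 among 13 patients at stage 1, and 2 versus 3 among 20 at the end.

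**Working it through.** **Who is exposed.** Assume undelayed 28-day cycles. C4D1 is day 3 × 28 + 1 = 85, C7D1 is day 6 × 28 + 1 = 169, and the 12-week minimum duration in Appendix B is 84 days.

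1. A patient who stops before about day 85 cannot have completed 12 weeks of benefit on drug, wherever the exit marrow falls.
2. A patient who reaches C7D1 has the scheduled marrow and formal assessment on drug.
3. Between those days, two provisions can document a response on drug. One is the C4D1 marrow, which footnote 7 lets the treating physician omit. The other is the milestone assessment in Section 12, available after Cycle 1, where clearance of circulating blasts prompts a marrow. Eligibility allows at least 10% blasts in blood or marrow, so a patient who qualifies on marrow alone, with no circulating blasts, cannot set off that trigger.
4. The exposed group is therefore those who stop roughly between days 85 and 168 with no response already documented by either route.

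An example, using the 1.9-month median time to first response that 6.3 gives for relapsed/refractory AML (a different disease, so illustrative only): 1.9 × 30.4 ≈ day 58, and 58 + 84 = day 142. A patient with that course who stops on day 150 has completed 12 weeks on drug. If the C4D1 marrow was waived and no milestone assessment was done, the first scheduled formal reading is near day 150 + 30 = 180. That is off drug and past the nominal sixth cycle (6 × 28 = day 168).

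**Size.** Inputs from 20.1 are a null rate of 5%, a target rate of 25%, 13 patients at stage 1 with closure at 0 responses, and success at 3 or more of 20. For true rate p:

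- P(early stop) = (1 − p)^13
- P(success) = P(Bin(20, p) ≥ 3) − (1 − p)^13 × P(Bin(7, p) ≥ 3)

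At p = 0.25, P(early stop) = 0.75^13 = 0.0238 and P(success) = 0.9087 − 0.0238 × 0.2436 = 0.903. At p = 0.05 the results are 0.513 and 0.074. Table 6 states 0.02 and 0.90, and 0.51 and 0.07, so the plan's figures reproduce.

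The documents give no rate of missed responses. If a share m of true responders were scored as non-responders, the effective rate would be 0.25 × (1 − m):

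| Assumed m | Effective rate | P(early stop) | P(success) |
|---|---|---|---|
| 0 | 0.250 | 0.024 | 0.903 |
| 10% | 0.225 | 0.036 | 0.854 |
| 20% | 0.200 | 0.055 | 0.786 |

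The same loss at a true rate of 5% lowers the effective rate, so type I error cannot rise above 0.074.

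**Spleen imaging.** CR and PR use palpation. CT or MRI confirms a spleen response, which feeds clinical improvement. That is an endpoint component in the chronic-phase cohort (20.2), not in the accelerated/blast-phase cohort.

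**The case against.** A reader might infer that every early leaver's primary response is read off drug or missed. The documents do not support that, for four reasons.

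- The C4D1 marrow and the milestone assessment can record a response before exit. They are conditional or waivable, so they narrow the exposed group without emptying it.
- The first PR route in Appendix B lists no marrow, only counts and clinical findings. Table 4 already collects blood counts, spleen and liver examination and the MF-SAF at End of Treatment. For that route only the formal assessment is missing.
- The 12-week rule makes the timing immaterial for very early leavers.
- The endpoint is best response, so a worse reading at End of Study does not overturn a response already documented. No extra rule in 20.1 is needed for that.

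A reader might also infer that the End of Study reading is contaminated by the next treatment. Section 15.2 brings the visit before any new anti-cancer therapy, although footnote 11 and 11.1 do not repeat that condition. Nor should the power figures be read as an expected loss, since no passage supports a 10% or 20% miss rate.

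Finally, the conflict is softer than a flat contradiction: the opening of 15.1 is ambiguous, Table 5's column heading agrees with Table 4, and only its footnote ties the sample to stopping drug. That is fair, but sites still lack one clear instruction.

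**Conclusion.** The inconsistency is real and worth correcting. It leaves a limited group of accelerated/blast-phase patients with their scheduled response reading about 30 days off drug: those who stop before C7D1, mainly after enough treatment to meet the 12-week rule, with no response documented on drug. For them an undocumented response becomes a non-response by rule.

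The resulting bias is downward and its size is unknown. It can cost power but cannot inflate type I error. The range 0.854 to 0.786, against 0.903, rests wholly on the assumed 10% to 20% loss. Spleen-imaging timing affects clinical improvement in the chronic-phase cohort and has no bearing on CR or PR.

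One caveat on the reading: the placement of the response assessment is taken from Table 4's columns alone, whereas footnotes 6 and 8 confirm marrow and imaging in words.

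**What to change.** Reconcile Table 4, including footnotes 6 and 8, with 15.1 and Table 5. For patients who stop before C7D1, move marrow and a formal response assessment from End of Study to the End of Treatment visit, and move spleen imaging likewise for the chronic-phase cohort. Add the response assessment to the 15.1 list and reword its opening sentence so that the list clearly belongs to that visit.

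This is a correction to the schedule that moves procedures and adds none. Its downside is one fewer later reading for confirming duration. For example, a response first seen at C4D1 (day 85) reaches 12 weeks on day 85 + 84 = 169, so for a patient stopping in Cycle 6 the later marrow might have helped. Counts, palpation and the MF-SAF would still be collected at End of Study under Table 4.
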